# **Background and rationale**

# **Background**

Uterine fibroids (myomas) are benign tumors that develop from the smooth muscular tissue of the uterus. The prevalence of uterine fibroids rises with age, affecting up to 70% of women in their fifth-sixth decades. Risk factors are represented by African ethnicity, nulliparity, obesity, and diabetes. Although many fibroids remain clinically silent, approximately 25-50% of women develop significant symptoms. The clinical presentation may include one or more of the following symptoms: menorrhagia/metrorrhagia, chronic pelvic pain, dysmenorrhea, and "bulky" symptoms. The number, size and location of the fibroids determine the severity of symptoms, which may lead to severe impairment of quality-life and cause risks in terms of general and reproductive health [1].

Myometrial lesions are non-cancerous neoplasms in almost all cases. Actually, the prevalence of unexpected sarcoma in women undergoing surgery for a myometrial lesion ranges from 1/2000 to 1/350. Preoperative diagnosis of malignant mesenchymal tumors of the uterus (Mesenchymal Uterine Malignancies, MUMs) remains a significant challenge. Our group recently identified and validated a diagnostic algorithm based on women's clinical characteristics and specific ultrasound parameters, which showed high accuracy in evaluating suspicious myometrial lesions [2]. Although ultrasound is the first-level diagnostic tool to evaluate women with myometrial lesions, data on ultrasound features of MUMs are mainly based on retrospective case series. Similarly, accurate diagnostic criteria able to discriminate between benign and malignant lesions have never been prospectively validated with magnetic resonance imaging (MRI) [2].

Recently the MUSA (Morphological Uterus Sonographic Assessment) consensus statement proposed the terms, definitions and measurements that may be used to describe and report the sonographic features of the myometrium. Myometrial pathology may be localized (one or more lesions) or diffuse (when > 50 % of the myometrium is involved). Each identified lesion should be described according to its location, size and site. The minimum distance from the lesion to the endometrium (inner lesion-free margin) and to the serosal surface (outer lesion-free margin) of the uterus should be reported [2-3].

A uterine fibroid typically appears on ultrasound as a well-defined round lesion within the myometrium or attached to it, with variable echogenicity, often showing shadows at the edge of the lesion and/or internal fan-shaped shadowing. On color- or power-Doppler imaging, circumferential flow around the lesion is often visible [2-3]. Vascularization is typically low to moderate on color Doppler (color score 2-3). Conversely, irregular margins, cystic areas, heterogeneous echotexture, and increased vascularization are some of the characteristics suggestive for atypical or suspicious myometrial lesion [2].

Stratifying patients based on the risk of malignancy is crucial for deciding subsequent therapeutic approaches. Currently, a wide range of treatments (pharmacological, surgical, interventional radiology) is available for women with myometrial lesions. Decision-making should be guided not only by the risk of malignancy but also by the type of symptoms, the severity of the clinical condition, age, and reproductive desires.

In premenopausal women, when abnormal uterine bleeding is the predominant symptom, one of the most effective options is the combination therapy of relugolix (an oral GnRH receptor antagonist), estradiol, and norethisterone (Ryeqo®). This combination aims at suppressing the hypothalamic-pituitary-ovarian axis to induce amenorrhea while providing a minimal hormonal supply in order to prevent the effects of complete estrogen deprivation (vasomotor symptoms, vulvovaginal atrophy, bone mass reduction).

Previous clinical studies on this drug have focused on its efficacy in reducing menstrual blood loss and alleviating pain symptoms in women with symptomatic fibroids. In particular, phase III studies reported that over 70% of patients treated with this drug experience a reduction in menstrual bleeding within the first 24 weeks of therapy. Furthermore, the safety profile of the relugolix-estradiol-norethisterone combination appears favorable, with a low risk of severe adverse events and good long-term tolerability [4][5][6].

Currently, the effects of this treatment on fibroid size, uterine volume, and, most importantly, on the ultrasound features remain unclear.

### Rationale

Based on the critical role of ultrasound evaluation in the diagnostic and therapeutic management of women with myometrial formations, the aim of this study is to analyze potential changes in ultrasound parameters during treatment with relugolix/estradiol/norethisterone. Specifically, the study aims at determining whether this pharmacological therapy can induce changes in myometrial formations that could impact patient stratification during the oncological risk assessment.

### **OBJECTIVES**

# Primary Objective

To observe the ultrasound features of myometrial lesions during treatment with relugolix/estradiol/norethisterone at baseline, and after 3 months, 6 months, and 12 months from treatment initiation, and to identify any change over time.

# Secondary Objectives

To observe during treatment with relugolix/estradiol/norethisterone, the effect on symptoms (e.g., abnormal uterine bleeding, pelvic discomfort, urinary disorders, dyschezia, dyspareunia, chronic pelvic pain and to record any adverse effect of the drug.

# **METHODS**

# Study design

Monocentric, observational study, ambispective study

# **Target Population**

Patients with ultrasound diagnosis of uterine fibroids, symptomatic for abnormal uterine bleeding, eligible for oral medical therapy with relugolix/estradiol/norethisterone. The retrospective cohort will be included starting from July 1st 2023.

# Study duration

3 years (2 years for enrollment and 1 year for follow-up)

### Inclusion criteria

- 1. Age  $\geq$  18 years.
- 2. Pre-menopausal status.
- 3. Ultrasound diagnosis of benign myometrial lesion.
- 4. Symptomatic patients presenting with abnormal uterine bleeding (menorrhagia/metrorrhagia).
- 5. Availability of ultrasound images in digital format.
- 6. Signature of Informed Consent

It is Specified that patients with a clinical indication for surgery may be included in the study if symptomatic for abnormal uterine bleeding.

#### Exclusion criteria

- 1. Age < 18 years.
- 2. Postmenopausal women.
- 3. Myometrial lesion  $\leq 10$  mm.
- 4. Myometrial formation suspected of malignancy on ultrasound (e.g., STUMP Uterine Leiomyosarcoma).
- 5. Asymptomatic patients with uterine fibromatosis.
- 6. Personal history of malignant or premalignant uterine neoplasia (e.g., STUMPs, leiomyosarcoma, atypical endometrial hyperplasia, endometrial carcinoma, cervical carcinoma).
- 7. Patients with ovarian pathology.
- 8. Patients currently undergoing treatment for another malignancy.
- 9. Patients lacking available digital ultrasound images or whose image quality is insufficient to adequately characterize the target lesion's ultrasound features.

Suspicious myometrial lesions are defined based on clinical experience and according to the criteria established by the Mylunar study (2).

# Variables and procedures

All women enrolled in the study will sign an informed consent form.

Patients retrospectively identified from the institutional registry may be included in the protocol if clinical data and ultrasound examinations are available, prior written consent. Recorded data will be retrieved from the examinations at baseline (before treatment) and 3 months, 6 months, and 12 months after treatment initiation.

Patients enrolled prospectively will be managed according to the activities and procedures depicted in Table 1. Clinical and ultrasound data will be recorded at baseline (before treatment) and 3 months, 6 months, and 12 months after treatment initiation.

Study data will be collected according to a dedicated eCRF that includes clinical, ultrasound, and pathological information (Appendix 1 MySaturn study).

The eCRF will be implemented using RED Cap platform (ref: https://projectredcap.org)

Study data will be collected and managed using REDCap electronic data capture tools hosted at Fondazione Policlinico Universitario A. Gemelli, IRCCS (https://redcap-irccs.policlinicogemelli.it/). REDCap (Research Electronic Data Capture) is a secure, web-based application designed to support data capture for research studies, providing 1) an intuitive interface for validated data entry; 2) audit trails for tracking data manipulation and export procedures; 3) automated export procedures for seamless data downloads to common statistical packages; and 4) procedures for importing data from external sources. People officially registered as study investigators or data managers will receive a user login to access the REDCap web platform and enter/manage data.

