# **Informed Consent**

Patients eligible for this study will be required to sign the Informed Consent Form in the context of a follow-up outpatient visit in which a study collaborator should be present. It will also be necessary to be able to use the data of patients who did not give Informed Consent because they are deceased, as failure to include this population would reduce the sample size producing negative consequences for the study in terms of significance of the results.

A copy of the written consent signed by the patient will be kept by the center in the appropriate section of the trial site file.

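### Retrospective entry can be read as requiring scans taken after treatment start, so the volume trend may come from women who completed follow-up

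*Protocol*

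**What the plan says.** The study is single-centre, single-group and ambispective. The primary endpoint is change in the volume of the index lesion during treatment.

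- **Retrospective entry** (Variables and procedures): "Patients retrospectively identified from the institutional registry may be included in the protocol if clinical data and ultrasound examinations are available, prior written consent". The sentence that follows reads: "Recorded data will be retrieved from the examinations at baseline (before treatment) and 3 months, 6 months, and 12 months after treatment initiation". Target Population gives the start: "The retrospective cohort will be included starting from July" 1, 2023.
- **Image criteria**: Inclusion item 5 requires "Availability of ultrasound images in digital format". Exclusion item 9 removes "Patients lacking available digital ultrasound images or whose image quality is insufficient" to characterise the target lesion. Neither names a time point.
- **Surgery** (Inclusion criteria): "patients with a clinical indication for surgery may be included in the study if symptomatic for abnormal uterine bleeding".
- **Analysis** (Statistical analysis): repeated-measures ANOVA for the time trend in quantitative variables. Handling of incomplete series is not mentioned.
- **Consent**: Inclusion item 6 and Variables and procedures have every enrolled woman sign. The Informed Consent section has patients "required to sign the Informed Consent Form in the context of a follow-up outpatient visit", and adds: "It will also be necessary to be able to use the data of patients who did not give Informed Consent because they are deceased".

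**The concern.** An abstractor working from the registry must decide what counts as having ultrasound examinations available. One could take every eligible woman with a usable scan before treatment. Another could take only women with the whole series, because the next sentence lists all four examinations. The two would build different cohorts from the same registry.

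On the stricter reading, entry depends on something that happens after treatment starts. A woman whose index lesion is removed before month 12 has no later scan of it and would be left out, although the inclusion criteria expressly admit women with an indication for surgery. The prospective schedule starts at a baseline before treatment, so those women enter before their later scans are known. The two parts of the study would then represent different populations.

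The time trend is itself the primary result, and no control group shares the selection. If staying in follow-up is related to how the lesion responds, the estimated trend is biased, and a larger sample does not remove that. Complete-case ANOVA would have the same effect even if entry were defined on the baseline scan alone.

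**Working it through.** **1. The plan's own figure.** Inputs from Sample size calculation: 4 time points, f = 0.10, correlation 0.6, two-way error rates of 5% and 20%, N = 111. Sphericity is assumed. The noncentrality is λ = N × 4 × f² / (1 − ρ) = 111 × 4 × 0.01 / 0.4 = 11.1, with 3 and 3 × 110 = 330 degrees of freedom. Power is 80.3% at N = 111 and 79.9% at N = 110, so 111 reproduces as the smallest adequate number.

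**2. The two readings side by side.**

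| Text | Supports all-scans entry | Supports baseline-only entry |
|---|---|---|
| Entry sentence, Variables and procedures | plural examinations, followed at once by the four-visit list | no time point named |
| Retrieval sentence | refers back to the examinations | can simply say where data come from |
| Inclusion item 5, Exclusion item 9 | not limited to baseline | not extended to follow-up |
| Women with a surgical indication admitted | – | those operated on before month 12 could not have all scans |

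Nothing in the document decides between the columns.

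**3. Possible effect on volume change (illustration; every input assumed).** Take as target the women with at least one on-treatment follow-up scan. Let s be the retrospective share, p the share of retrospective women not entered, m = s × p, and h the non-entrants' mean change as a fraction of the entrants'. All prospective women are taken to enter. The relative error of the entrants' mean is 1 / (1 − m + m × h) − 1.

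| h | s = 0.5, p = 0.2 (m = 0.10) | s = 0.25, p = 0.2 (m = 0.05) |
|---|---|---|
| 1 | 0% | 0% |
| 0.5 | 1/0.95 − 1 = 5.3% | 1/0.975 − 1 = 2.6% |
| 0 | 1/0.90 − 1 = 11.1% | 1/0.95 − 1 = 5.3% |
| 1.5 | 1/1.05 − 1 = −4.8% | 1/1.025 − 1 = −2.4% |

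The row h = 0 is the extreme unless lesions grow in the women left out. The protocol gives neither the retrospective share nor the share lost, so the table shows only how the error behaves.

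**4. What complete-case analysis would cost in power.** If 10%, 20% or 30% of 111 women (assumed) lacked a scan, then 99, 88 or 77 complete cases remain, rounding down. By the formula in step 1, power is 75.0%, 69.3% or 62.7%. Keeping 111 complete cases would need 111/0.9, 111/0.8 or 111/0.7, rounded up to 124, 139 or 159 women. These figures measure lost precision, not the bias in step 3.

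**The case against.** The strongest reply is that the four-visit list says where data come from, not who is eligible. The prospective cohort gets the same list in a parallel sentence, and nobody would read that one as an entry condition. The case report form also holds pathological information, and women with a surgical indication are admitted, which suggests that operated women are expected in the data. This stands in part. It makes the baseline-only reading quite plausible, but not certain, since surgery could follow month 12 and the entry sentence still leaves the examinations undefined.

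It can also be said that missing-data handling belongs in an SAP, which is not shown. That is fair as to detail. The protocol does name the method, however, and repeated-measures ANOVA in its usual form drops incomplete series. The concern is conditional on that use.

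A reader might infer more than the document supports:

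- *That all four scans are required.* No sentence says so.
- *That volume reduction will be overstated.* The direction is unknown, and the bias is zero if leaving is unrelated to response. Women who stopped before month 3 have no on-treatment follow-up scan in the schedule, so they bear little on an endpoint defined during treatment.
- *That adverse effects will be under-counted by a known amount.* The protocol only says they will be recorded. It defines no incidence endpoint and gives no rates.
- *That the consent rule shuts out women who stopped treatment.* The visit is not specified and continued treatment is not required, so those who still attend can sign. No route is stated for living women who no longer attend, but consent pages are not in the copy at hand and the answer depends on ethics rules outside it.
- *That women left out are lost for good.* They are identified from a registry, so they can be counted and, with consent, added.

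**Conclusion.** The concern holds as an ambiguity worth removing, not as a demonstrated bias. As written, the retrospective entry condition allows selection on scans obtained after treatment start, and ANOVA on complete cases would reinforce it. Both effects would make the volume trend that of women who completed follow-up.

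The size and direction cannot be determined from the document. The illustrative range of −4.8% to 11.1% rests wholly on assumed shares and responses, and it shrinks with the retrospective share of the sample. If the sponsor already intends baseline-only entry, one sentence settles the first part. The stated sample size needs no correction on this account.

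**What to change.** 1. **Variables and procedures**: define the retrospective cohort as all consecutive eligible women who started treatment from 1 July 2023 and have a usable baseline scan, whether or not later scans exist.
2. **Inclusion item 5 and Exclusion item 9**: apply them to the baseline scan only. Treat a missing or poor-quality follow-up scan as a missing value at that visit, not as a reason for exclusion.
3. **Statistical analysis**: for lesion volume, replace repeated-measures ANOVA with a linear mixed model using all available scans.
4. **Reporting**: state how many registry women were identified, how many were not entered, and why.
5. **Secondary wording point**: reconcile the rule that every enrolled woman signs (Inclusion item 6, Variables and procedures) with the exception for deceased patients in Informed Consent. Ask the ethics committee how consent may be handled for living women who no longer attend.

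The cost is a few sentences of protocol text and one question to the ethics committee. The downside is more incomplete records, and women with only a baseline scan add little information on change. A mixed model loses less power than the complete-case figures above, but it relies on missingness being explained by the observed data and cannot correct for women who were never entered. Items 1, 2 and 4 are therefore needed alongside it.

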#### **ENDPOINTS**

# Primary endpoint

Modifications in the volume of the index myometrial lesion during treatment with relugolix/estradiol/norethisterone;

# Secondary endpoints (referred to the primary objectives)

Description of the ultrasound characteristics of the fibroids in the study population during treatment with relugolix/estradiol/norethisterone.

Based on current literature, the following features have been preselected for analysis:

- Max diameter of the index myometrial lesion
- Uterine volume
- Outer contour: regular or irregular;
- Echogenicity of the myometrial formation: mixed or homogeneous;
- Presence of cystic areas;
- Presence of acoustic shadows;
- Vascularization of the lesions, expressed on a 1 to 4 ordinal scale;
- "Cooked aspect."

Volume of the index myometrial lesion is considered the primary endpoint of this study and the other features as key secondary endpoints.

### Secondary endpoints (referred to the secondary objectives)

Description of the clinical characteristics of the study population during treatment with relugolix/estradiol/norethisterone. The following clinical variables will be recorded:

- Effect on abnormal uterine bleeding, measured as the number of sanitary pads used during the cycle in patients who do not develop amenorrhea;
- Hemoglobin, serum iron, and ferritin levels at baseline, 3, 6, and 12 months;
- Dyspareunia, assessed using NRS or VAS scales;
- Chronic pelvic pain, assessed using NRS or VAS scales;
- Compression-related symptoms;
- Pollakiuria and dyschezia;
- Dyspareunia;

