### Statistical analysis

Descriptive analyses of patients' characteristics will be provided. For continuous variables, the mean and standard deviation (SD) or the median and interquartile range (IQR) will be calculated as appropriate. The normality assumption about the distribution of continuous variables will be tested using the Kolmogorov-Smirnov test. Categorical variables will be summarized with frequencies absolute counts and percentages. Repeated measures ANOVA will be implemented to assess temporal trend in quantitative variables while dichotomous items will be analyzed using a mixed-effect generalized linear model. All statistical analysis will be performed using R software (www.r-project.org).

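### The only direct bleeding endpoint leaves out women who become amenorrhoeic, and no listed endpoint counts them

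*Protocol*

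**What the plan says.** - **Objective.** The Protocol, Secondary Objectives, asks for "the effect on symptoms (e.g., abnormal uterine bleeding, pelvic discomfort, urinary disorders" and further symptoms. Bleeding is the first example, and no subgroup is named.
- **Population.** Under Inclusion criteria every woman must have this symptom at entry: "Symptomatic patients presenting with abnormal uterine bleeding (menorrhagia/metrorrhagia".
- **Aim of the drug.** The Background states: "This combination aims at suppressing the hypothalamic-pituitary-ovarian axis to induce amenorrhea".
- **Endpoint.** Secondary endpoints (referred to the secondary objectives) opens by promising a "Description of the clinical characteristics of the study population during treatment with relugolix/estradiol/norethisterone". Its bleeding item is then "measured as the number of sanitary pads used during the cycle in patients who do not develop amenorrhea".
- **Related measure.** The same list has "Hemoglobin, serum iron, and ferritin levels at baseline, 3, 6, and 12 months", without restriction to any group of women.
- **Analysis.** Under Statistical analysis, quantitative variables go to repeated measures ANOVA, and "dichotomous items will be analyzed using a mixed-effect generalized linear model".

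**The concern.** Whether a woman becomes amenorrhoeic is known only after treatment starts, and it is the response that the drug is meant to produce. An endpoint confined to women without that response describes only partial responders and non-responders on bleeding. The more women respond completely, the fewer the endpoint counts.

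The text also does not say whether a woman is dropped altogether once she becomes amenorrhoeic (by patient) or only at the visits where she is amenorrhoeic (by visit). By visit, the women counted can differ between 3, 6 and 12 months, so a time trend would mix change on treatment with change of membership.

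At stake is the answer to the symptom objective for the symptom that every participant has at entry. This is a rule that the Protocol states, not a detail left to a later plan.

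**Working it through.** **Which endpoints cover women with amenorrhoea**

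| Listed endpoint | Direct measure of bleeding? | Covers women with amenorrhoea? |
|---|---|---|
| Lesion volume (primary) and other ultrasound features | No | Yes |
| Pads per cycle | Yes | No |
| Hemoglobin, serum iron, ferritin | No, indirect | Yes |
| Pain, compression, urinary, bowel symptoms, dyspareunia | No | Yes |
| Amenorrhoea | Yes | Not listed |

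**The plan's own figure.** N = 111 belongs to the primary endpoint. For one group with 4 time-points, f = 0.10 and correlation 0.6, the noncentrality is n × 4 × f² / (1 − 0.6) = 111 × 4 × 0.01 / 0.4 = 11.1, with 3 and 330 degrees of freedom. Power is 0.803 at n = 111 and 0.799 at n = 110, so 111 reproduces. Nothing below changes it.

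**Size of the distortion.** The Protocol gives no amenorrhoea rate and no pad count, so all inputs here are assumed. The unit is the mean baseline pad count of the women who stay in the endpoint.

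- a = share of women excluded
- r = fraction of baseline pads that the others still use, set at 0.6
- k = baseline of the excluded women relative to the others
- s = fraction of baseline pads that the excluded women use at the visit analysed (0 if amenorrhoeic then)
- B = (1 − a) + a·k = mean baseline in all women

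Exclusion by patient, or a paired by-visit comparison of each woman with her own baseline, reports 1 − r. All women give 1 − [(1 − a)·r + a·k·s]/B. The difference, all women minus reported, is a·k·(r − s)/B.

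*Visit at which the excluded women are amenorrhoeic (s = 0).* The difference is r·a·k/B, which is positive. With k = 1 (B = 1):

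| a | Reported | All women |
|---|---|---|
| 0.3 | 40% | 1 − 0.7 × 0.6 = 58% |
| 0.5 | 40% | 1 − 0.5 × 0.6 = 70% |
| 0.7 | 40% | 1 − 0.3 × 0.6 = 82% |

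The reported figure cannot tell these three situations apart. With unequal baselines at a = 0.5, k = 0.4 (B = 0.70) gives 57% and k = 1.5 (B = 1.25) gives 76% in all women, again against 40%.

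*Earlier visit, exclusion by patient.* A woman who becomes amenorrhoeic at 12 months is then also missing at 3 months, when she may still bleed. If s > r the sign reverses. With a = 0.5, k = 1 and s = 0.8, all women show 1 − (0.3 + 0.4) = 30% against 40% reported.

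*Absolute scale (s = 0; by patient or paired).* All women lose B − (1 − a)·r and the endpoint reports 1 − r, so the difference is a·(k + r − 1). At a = 0.5 it is −0.10, 0.00, 0.30 and 0.55 for k = 0.2, 0.4, 1 and 1.5. Understatement needs k > 1 − r.

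**Women left in the endpoint.** If 33, 56 or 78 of 111 are amenorrhoeic (about 30%, 50% or 70%), 78, 55 or 33 remain.

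**The case against.** **The item may only list a recorded variable.** The endpoint section says that clinical variables will be recorded, and pads per cycle has no plain meaning in a woman without a cycle. The clause may therefore just mark where the count applies. Applying it also requires knowing who is amenorrhoeic. Part of this stands: Table 1 and the eCRF are not shown, and amenorrhoea may well be a field in them. A reader might infer that it is not collected, and the Protocol does not support that. But a recorded field is not a listed endpoint, and on either reading no endpoint covers bleeding in these women. Zero pads is also a valid value over a stated period.

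**Hemoglobin, iron and ferritin cover everyone.** True, but they reflect bleeding only indirectly.

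**The direction of bias is not fixed.** This stands. A reader might infer that the pad result always understates the benefit. That holds for the percentage reduction at a visit where the excluded women use 0 pads and the others still use some. It can fail at earlier visits under exclusion by patient. On the absolute scale it depends on the excluded women's baseline. The repeated measures ANOVA that the Protocol plans is a within-woman comparison, to which the paired formula applies.

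**The figures come from no trial data.** This also stands. The Protocol does not define a percentage reduction in pads, so they only illustrate.

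**It is one descriptive secondary item in an observational study focused on ultrasound.** Agreed, and this limits the weight of the point.

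**Conclusion.** The point holds and should be fixed. The only direct bleeding endpoint is defined on a subgroup chosen by a result of treatment. It omits complete responders on bleeding, and no other listed endpoint counts them. The pad result therefore cannot answer the unrestricted symptom objective.

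This conclusion rests on the wording alone. The size rests on assumptions: with r = 0.6, equal baselines and excluded women at 0 pads, the shortfall is 18, 30 or 42 percentage points (58, 70 or 82 minus 40). No claim is made that the bias always runs one way. A reader might also infer that the primary analysis is weakened, but lesion volume has no such restriction, and N = 111 does not depend on pads.

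**What to change.** 1. **List amenorrhoea as a secondary endpoint:** the proportion of women with amenorrhoea at 3, 6 and 12 months among all treated women, using the mixed-effect generalized linear model already planned for dichotomous items.
2. **Define the pad endpoint in all treated women,** with amenorrhoea counted as 0 pads, over a fixed window where prospective data allow. Keep pads among women still bleeding as a labelled descriptive supplement, and say whether that exclusion is by patient or by visit.
3. **Report the number with unknown amenorrhoea status** at each visit, separately for the retrospective and prospective cohorts.

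**Cost.** The wording change is small and N stays at 111. With status known for all women, the Wilson 95% interval would be 22–39% for 33/111, 41–60% for 56/111 and 61–78% for 78/111.

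There are two real downsides. First, a pad count with many zeros does not suit repeated measures ANOVA. The Protocol should exempt it from that rule and allow a model or summary suited to zeros, with the details left to the SAP. Second, Variables and procedures relies on existing records for the retrospective cohort ("Recorded data will be retrieved from the examinations at baseline (before treatment" and at the later visits), so pad counts or amenorrhoea status may be incomplete there and a fixed window may not be obtainable. As an assumed example, if status is unknown in 22 of 111 and 45 of the other 89 are amenorrhoeic, the estimate is 51% (95% interval 40–61%). Counting all 22 as not amenorrhoeic gives 45/111 = 41%, and counting all as amenorrhoeic gives 67/111 = 60%.
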